2.4.4.3 Multiplicity issues

For the primary efficacy analysis in Phase 2, one hypothesis is to be tested on each of the 2 dose arms. To control overall type I error, Hochberg procedure will be used. The procedure is described in [Section 2.4.4.1](#). An interim analysis is included to stop a dose arm for futility only, thus the type I error rate is not inflated.

2.4.5 Analyses of safety data

All safety analyses will be performed on the AT/safety population as defined in [Section 2.3.2](#).

2.4.5.1 Dose-limiting toxicities (Phase 1 only)

The DLTs will be listed by patient on the patients evaluable for DLT population for Phase 1.

2.4.5.2 Analyses of adverse events

The primary focus of adverse event analysis will be on treatment-emergent adverse events. Pre-treatment and post-treatment AEs will be described separately.

If an AE date of onset (occurrence, worsening, or becoming serious) is incomplete, an imputation algorithm will be used to classify the AE as pretreatment, treatment-emergent, or post-treatment. The algorithm for imputing date of onset will be conservative and will classify an AE as treatment emergent unless there is definitive information to determine it is pretreatment or post-treatment. Details on classification of adverse events with missing or partial onset dates are provided in [Section 2.5.3](#).

For patients with multiple occurrences of the same AE within the observation period (pre-treatment, on-treatment and post-treatment), the maximum severity grade will be used. Summaries will be provided for all grades and for Grade ≥ 3 (including Grade 5). Missing grade handling is provided in [Section 2.5.3](#).

The following adverse events analyses will be performed. The presentation strategy (eg, by all grades and Grade ≥ 3 and by PT etc) are included in [Table 7](#).

- Overview of TEAEs.
- TEAEs (regardless relationship to study treatment).
- Drug related TEAEs.
- Deaths ([Section 2.4.5.3](#)).
- SAEs.
- Adverse events leading to withdrawal.
 - Analysis of all treatment-emergent adverse event(s) leading to definitive treatment discontinuation. Analysis of all treatment-emergent adverse event(s) leading to premature isatuximab discontinuation. Analysis of all treatment-emergent adverse event(s) leading to premature cemiplimab discontinuation. If the number of patients who discontinued treatment due to a TEAE is ≤ 5 , no summary table will be provided. Instead, listing(s) will be provided.
- TEAE leading to dose modification
 - Separate analysis for each type of modification: dose reduction of any drug, dose interruption of any drug, dose delay of any drug.

- Other significant adverse events
 - IR and IR symptoms (details are included below),
 - Immune related AEs (details are included below),
 - Respiratory AEs(details are included below),
 - Hematological adverse events(details are included below; not included in [Table 7](#)),
 - Second primary malignancies,
 - Other AESIs:
Pregnancy and symptomatic overdose. Data will be listed if ≤ 5 patients,
 - Pre- and Post-treatment AE/SAEs.

Sorting within tables will ensure the same presentation for the set of all AEs within the observation period (pre-treatment, on-treatment, and post-treatment). For that purpose, the table of all TEAEs presented by SOC and PT sorted by the internationally agreed SOC order and decreasing frequency of PTs within SOCs will define the presentation order for all other tables unless otherwise specified. Sorting will be based on the incidence of AEs of the isatuximab QW/Q2W plus cemiplimab Q2W arm.

Overview of TEAEs

An overview of TEAEs including the number (%) of patients with the following treatment emergent events will be provided:

- TEAE.
- TEAE of Grade ≥ 3 .
- TEAE of Grade 3-4.
- TEAE of Grade 5 (any TEAE with fatal outcome during the on-treatment period).
- Treatment emergent SAE.
- TEAE leading to definitive study treatment discontinuation, ie, discontinuation of isatuximab in control arm, and discontinuation of isatuximab and cemiplimab in combination arms.
- TEAE leading to premature discontinuation (only applicable to combination arms)
 - TEAE leading to premature isatuximab discontinuation, ie, discontinuation of isatuximab before cemiplimab,
 - TEAE leading to premature cemiplimab discontinuation, ie, discontinuation of cemiplimab before isatuximab.
- AESI
 - IR of Grade ≥ 2 .
- Treatment-related TEAE (related to either isatuximab or cemiplimab).
- Treatment-related TEAE of Grade ≥ 3 .
- Serious treatment-related TEAE.

Other significant adverse events

Infusion reactions

IR analyses will be done by including all the adverse events regardless of relationship to isatuximab, cemiplimab or NIMP. Unless otherwise described, the presentation strategy is described in [Table 7](#).

- Number (%) of patients experiencing IRs (as a diagnosis, no symptoms) according to investigator reported AEs presented by primary SOC and PT (both sorted by decreasing order of frequency) will be summarized by grades (all grades and Grade ≥ 3).
- Description of the IR diagnoses (using the diagnosis reported and excluding symptoms)
 - Worst grade,
 - Action taken with isatuximab and cemiplimab,
 - Number (%) of patients with only 1, ≥ 1 , ≥ 2 , ≥ 3 , ≥ 4 and ≥ 5 episodes,
 - Number (%) of patients with first occurrence of IR at the first infusion and subsequent infusions,
 - Number (%) of patients with IR at the first and subsequent infusions,
 - Number (%) of patients with at least two episodes of IRs at the same infusion,
 - Day of onset from infusion,
 - Duration (in days).
- Number of patients with symptoms of IRs (as reported by investigator).
- Number (%) of patients experiencing TEAEs (related and regardless of causal relationship) within 24 hours from the start of each infusion.
- Similar tables including all TEAEs within 24 hours from the start of each infusion from the selected list of CMQ (see [Section 2.1.4.1](#)).
- Number (%) of patients experiencing TEAEs (related and regardless of causality), (not only limited to those occurring within 24h of each infusion) from the selected list of CMQ (see [Section 2.1.4.1](#)).

If the IR rate is much higher ($\geq 20\%$) in combination arms than in the control arm, additional analyses of IR might be performed separately for isatuximab and cemiplimab.

A listing of IRs that are related to NIMP will be provided.

Immune related AEs:

Because irAEs could occur long after exposure with immune checkpoint inhibitors, the irAE analysis will include both on-treatment period and extended safety follow up period. As noted in [Table 7](#), the analysis will include:

- Number (%) of patients experiencing irAEs reported as AESI by investigator: include all AESI and exclude IRs, pregnancy, symptomatic overdose and DLT (if any).
- Number (%) of patients experiencing AEs from selected grouping of PTs occurring during the treatment emergent and extended safety follow up periods (one analysis for events related to cemiplimab; another analysis for regardless of relationship).
- Number (%) of patients experiencing AEs occurring during the treatment emergent and extended safety follow up periods (one analysis for events related to cemiplimab; another analysis for events regardless of relationship).

Respiratory TEAEs:

Respiratory TEAEs will be analyzed using selection defined in [Section 2.1.4.1](#) and will be presented by PT.

Cardiac TEAEs

Cardiac TEAEs will be analyzed using selection defined in [Section 2.1.4.1](#) and will be presented by PT, sorted by decreasing incidence.

Analysis of pre-treatment and post-treatment adverse events

The following frequency distributions of AEs (incidence tables) will be provided for the safety population, for all grades combined and Grade ≥ 3 :

- All pre-treatment AEs by primary SOC and PT, showing the number (%) of patients with at least 1 pre-treatment AE, sorted by the internationally agreed SOC order and decreasing incidence of PTs within each SOC.
- All pre-treatment SAEs by primary SOC and PT, showing the number (%) of patients with at least 1 pre-treatment SAE, sorted by the internationally agreed SOC order and decreasing incidence of PTs within each SOC.
- All post-treatment AEs by primary SOC and PT, showing the number (%) of patients with at least 1 post-treatment AE, sorted by the internationally agreed SOC order and decreasing incidence of PTs within each SOC.
- All post-treatment SAEs by primary SOC and PT, showing the number (%) of patients with at least 1 post-treatment SAE, sorted by the internationally agreed SOC order and decreasing incidence of PTs within each SOC.

Neutropenia and neutropenic complications

Neutropenia (from laboratory abnormalities) will be displayed along with febrile neutropenia and neutropenic infections (see [Section 2.1.4.1](#)).

Thrombocytopenia and hemorrhages

The number (%) of patients will be provided for:

- On-treatment thrombocytopenia (Lab) identified through grading of laboratory data per the NCI-CTCAE 4.03, by grade.
- Hemorrhages as defined in [Section 2.1.4.1](#) by grade.
- Hemorrhages following Grades 4 thrombocytopenia (Lab). The first hemorrhages event occurring within 8 days after any occurrence of the thrombocytopenia (Lab) will be used for this analysis.

Hemolytic disorders

Hemolytic disorders that occurred within 8 days after the blood cell transfusion will be analyzed using selection defined in [Section 2.1.4.1](#) and will be presented by PT.

- A listing of patients with hemolytic disorders will be provided. This listing will include the PT, study day of diagnosis (from first dose of study treatment), interval to onset from the last study treatment before the diagnosis (last drug administered), duration of AE, the cycle of occurrence, severity, seriousness, outcome, action taken on study treatment, study day of the blood transfusion, and results and sampling date of indirect anti-globulin test.

Overdose

A listing of patients who reported symptomatic overdose with study treatment during the study will be provided. This listing will include drug with overdose.

Pregnancy

Moreover, a listing of pregnancies (pregnancy as well as pregnancy of partner) will be provided.

Tumor lysis syndrome (TLS)

A listing of patients with TLS reported in eCRF AE forms (using a CMQ: Tumor lysis syndrome) during the study will be provided. The clinical chemistry parameters regarding hyperkalemia, hyperphosphatemia, hypocalcemia, and hyperuricemia might be listed to corroborate any report of TLS identified with the above CMQ.

Second primary malignancies

A listing of patients who reported second primary malignancies during the study will be provided (as per the CMQ).

This listing will include the diagnosis, type of second primary malignancies, study day of the diagnosis (from the first dose), number of days from the last study treatment to the diagnosis, prior exposure to anti-myeloma treatments, and whether the patient received subsequent anti-cancer treatment.

Table 7 - Description of summary tables to be provided for the analysis of TEAEs

MedDRA variables	Sorting	Layout	Events
PT	
 PT: Decreasing order of frequency of Isa + CemQ2W arm 	
By treatment arms (and all patients if Phase 1): n (%) of patients with any event and n (%) of patients with event of Grade ≥3
	
 TEAEs occurring in ≥5% of the patients (in any group for Phase 2) Cardiac TEAEs Respiratory TEAEs
SOC, HLG, HLT, and PT	
 Primary SOC: internationally agreed order HLG, HLT, PT: alphabetical order 	
By treatment arms (and all patients if Phase 1): n (%) of patients with any event and n (%) of patients with event of Grade ≥3
	
 All TEAEs Serious TEAEs Drug-related serious TEAEs TEAEs leading to definitive treatment discontinuation
SOC and PT	
 Primary SOC: internationally agreed order PT: decreasing order of frequency of Isa + CemQ2W arm 	
By treatment arms (and all patients if Phase 1): n (%) of patients with any event and n (%) of patients with event of Grade ≥3
	
 All TEAEs TEAEs occurring in ≥5% of the patients (in any group for Phase 2) Drug-related TEAEs Serious TEAEs Drug related serious TEAEs TEAEs leading to isatuximab discontinuation TEAEs leading to cemiplimab discontinuation TEAEs leading to dose interruption of isatuximab TEAEs leading to dose interruption of cemiplimab TEAEs leading to dose delay of isatuximab TEAEs leading to dose delay of cemiplimab TEAEs leading to dose reduction^a of isatuximab TEAEs leading to dose reduction^a of cemiplimab Pre-treatment AEs; Serious pre-treatment AEs Post-treatment AEs; Serious post-treatment AEs

MedDRA variables	Sorting	Layout	Events
SOC and PT	
 Primary SOC: internationally agreed order PT: decreasing order of frequency of Isa + CemQ2W arm 	
By treatment arms (and all patients if Phase 1): n (%) of patients with any event and n (%) of patients with event of Grade ≥ 3
	
IR analysis:
 
 IR diagnosis (as reported by investigator) Symptoms of IR (as reported by investigator) TEAEs (related; regardless of relationship) within 24 hours from the start of each infusion TEAEs (related; regardless of relationship) from the selected CMQ within 24 hours from the start of each infusion TEAEs (related; regardless of relationship) from the selected CMQ (not limited to those occurring within 24 hours from the start of each isatuximab infusion)
SOC and PT	
 Primary SOC: internationally agreed order PT: decreasing order of frequency of Isa + CemQ2W arm 	
By treatment arms (and all patients if Phase 1): n (%) of patients with any event and n (%) of patients with event of Grade ≥ 3
	
irAE analysis:
 
 irAE reported as AESI by investigator AEs as defined by irAE selected grouping of AEs occurring during the treatment emergent and extended safety follow up periods (related to cemiplimab; regardless of relationship) AEs occurring during the treatment emergent and extended safety follow up periods (related to cemiplimab; regardless of relationship)

a Dose reduction is corresponding to action taken to any study treatment, as "Dose reduced", "Dose delayed and reduced".

AE=adverse event; AESI=adverse event of special interest; HLGT=high-level group term; HLT=high-level term; IR=infusion reaction; MedDRA=Medical Dictionary for Regulatory Activities; n (%)=number and percentage of patients; PT=preferred term; SOC=system organ class; TEAE=treatment-emergent adverse event.

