4.1.2 PD-1

The importance of intact immune surveillance in controlling outgrowth of neoplastic transformation has been known for decades (6). The PD-1 receptor-ligand interaction is a major pathway hijacked by tumors to suppress immune control (7). The normal function of PD-1, expressed on the cell surface of activated T cells under healthy conditions, is to down-modulate unwanted or excessive immune responses, including autoimmune reactions. PD-1 (encoded by the gene *Pdcd1*) is an Ig superfamily member related to CD28 and CTLA-4, which has been shown to negatively regulate antigen receptor signaling upon engagement of its ligands (PD-L1 and/or PD-L2). The structures of murine PD-1 alone (8) and in complex with its ligands were first resolved (9, 10) and more recently the NMR-based structure of the human PD-1 extracellular region and analyses of its interactions with its ligands were also reported (11). PD-1 and family members are type I transmembrane glycoproteins containing an Ig Variable-type (V-type) domain responsible for ligand binding and a cytoplasmic tail which is responsible for the binding of signaling molecules. The cytoplasmic tail of PD-1 contains 2 tyrosine-based signaling motifs, an immunoreceptor tyrosine-based inhibition motif (ITIM) and an immunoreceptor tyrosine-based switch motif (ITSM). Following T cell stimulation, PD-1 recruits the tyrosine phosphatases SHP-1 and SHP-2 to the ITSM motif within its cytoplasmic tail, leading to the dephosphorylation

of effector molecules, such as CD3 ζ , PKC θ and ZAP70, which are involved in the CD3 T cell signaling cascade (12). The mechanism by which PD-1 down-modulates T cell responses is similar to, but distinct from that of CTLA-4 (13). PD-1 was shown to be expressed on activated lymphocytes, including peripheral CD4⁺ and CD8⁺ T cells, B cells, T regs and Natural Killer cells (14). Expression has also been shown during thymic development on CD4-CD8- (double negative) T cells (15) as well as subsets of macrophages (16) and dendritic cells (17). The ligands for PD-1 (PD-L1 and PD-L2) are constitutively expressed or can be induced in a variety of cell types (18). PD-L1 is expressed at low levels on various non-hematopoietic tissues, most notably on vascular endothelium, whereas PD-L2 protein is only detectably expressed on antigen-presenting cells found in lymphoid tissue or chronic inflammatory environments (18).

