and with all IAT methods (eg, gel, tube, solid phase). Agglutination reactions caused by anti-CD38 are usually weak (1+), but stronger reactions (up to 4+) may be seen in solid-phase testing. However, anti-CD38 does NOT interfere with ABO/RhD typing or with immediate-spin crossmatches.

Other notes on anti-CD38 serologic interference:

- Adsorptions using either untreated or ZZAP-treated cells fail to eliminate the interference.
- Anti-CD38 variably interferes with direct antiglobulin tests (DATs) and antibody identification panel autocontrols.
- Some rare Lu(a-b-) cells are not reactive in the presence of anti-CD38, potentially giving the false impression that the patient has a Lutheran-related antibody.^{4,5}
- Positive IATs can be observed for up to six months after anti-CD38 is discontinued.^{1,3}
- Anti-CD38 may cause a small decrease in hemoglobin in vivo (~1 g/dL), but severe hemolysis has not been observed among treated patients.^{3,6}

Anti-CD38 interference can cause delays in issuing RBCs

If the transfusion service is unaware that a patient has received anti-CD38, the following scenario may occur when the patient's sample is tested:

1. ABO/RhD typing: no issues.
2. Antibody detection (screening) test: all cells positive.
3. Antibody identification panel: all cells positive (autocontrol may be negative).
4. DAT: positive or negative.
5. AHG crossmatches: positive with all RBC units tested.
6. Adsorptions: panreactivity cannot be eliminated.

This leads to delays in issuing RBCs to the patient. In some cases, the anti-CD38 interference could mask the presence of a clinically significant alloantibody.

Recommendations

To avoid problems with transfusion, hospitals should set up procedures to inform the transfusion service whenever any patient is scheduled to begin taking anti-CD38.

BEFORE a patient begins taking anti-CD38:

- A baseline type and screen should be performed.
- In addition, a baseline phenotype or genotype is recommended.

AFTER a patient begins taking anti-CD38:

- ABO/RhD typing can be performed normally.
- For antibody detection (screening) and identification, dithiothreitol (DTT)-treated cells can be used to eliminate the interference.^{2,7}
 - Because DTT treatment destroys Kell antigens, K-negative units should be provided unless the patient is known to be K-positive.

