- TEAEs plus extended safety follow-up AEs from sponsor selected grouping of PTs (related to cemiplimab; regardless of relationship).

Respiratory AEs

Analysis of respiratory TEAEs will focus particularly on the following groupings:

- Lower Respiratory adverse events, selected using CMQ ‘Lower respiratory events’.
- Respiratory infections, selected using CMQ ‘Respiratory infections’.

In addition, respiratory adverse events with late onset (ie, occurring, worsening or becoming serious more than 30 days after last dose) will be analyzed as part of the post-TEAEs analysis.

Cardiac AEs

Analysis of cardiac adverse events will focus particularly on SMQ “Cardiac failure” (narrow).

Neutropenia and neutropenic complications

Neutropenia, febrile neutropenia and neutropenic infections will be analyzed using the following data source:

- Neutropenia based on laboratory results.
- Febrile neutropenia selected using CMQ ‘Febrile neutropenia’.
- Neutropenic infections: defined as NCI-CTCAE Grade ≥ 2 infections from SOC Infections and Infestations’ (selected using CMQ ‘GLB_SOC infections and infestations’) concomitant with NCI-CTCAE Grade 3-4 neutropenia from laboratory results. Infection and Grade 3-4 neutropenia will be considered as concomitant if one of the following condition is met:
 - Neutrophils count value measured the day of the start of the AE infection,
 - The last neutrophils count value measured before the start date of the AE infection is within 7 days before the start of the AE infection,
 - The first neutrophils count value measured after the start date of the AE infection is within 2 days after the start of the AE infection.

Thrombocytopenia and hemorrhages

- Thrombocytopenia will be analyzed based on laboratory results.
- Hemorrhages will be selected using the TEAEs from the SMQ ‘Haemorrhage terms (excl laboratory terms)’.
- Moreover, severe thrombocytopenia (ie, \geq Grade 4) with concomitant hemorrhage will be displayed if relevant. The first hemorrhages event occurring within 8 days after any occurrence of the thrombocytopenia (Lab) will be used for this analysis.

Hemolytic disorders

Hemolytic disorders will be selected using the TEAEs from the CMQ ‘Haemolytic disorders Broad’.

Tumor lysis syndrome

Tumor lysis syndrome will be identified using CMQ ‘Tumour lysis syndrome’.

Second primary malignancies

Second primary malignancies will be selected using CMQ ‘Second primary malignancies’

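### The dedicated hemolytic-disorder summary is limited to events within 8 days after a transfusion, without explanation, so no full CMQ-level hemolysis count is planned

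*SAP*

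**What the plan says.** SAP 2.1.4.1 gives the selection rule: "Hemolytic disorders will be selected using the TEAEs from the CMQ" for hemolytic disorders, in its broad version. It attaches no time window and does not mention transfusion.

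SAP 2.4.5.2, under its hemolytic-disorders entry, uses that selection with an added condition: "Hemolytic disorders that occurred within 8 days after the blood cell transfusion will be analyzed", by reference to Section 2.1.4.1 and with results shown by PT. The bullet beneath it reads "A listing of patients with hemolytic disorders will be provided". The listing's columns include "interval to onset from the last study treatment before the diagnosis (last drug administered), duration of AE, the cycle of occurrence", the day of the transfusion and the indirect antiglobulin result. The bullet states no window.

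Earlier in 2.4.5.2, hematological adverse events are named among the other significant events, with a note that they are not part of Table 7. Under SAP 2.4, Phase 2 summary tables are laid out by the three treatment arms.

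**The concern.** Followed exactly, the rule gives an incomplete count of the group of events it names. A reader of the study report who turns to the hemolysis summary will see only events that closely followed a transfusion, and may take that for the total.

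The restriction is suited to one question, reactions after transfusion in patients whose blood typing is disturbed by an anti-CD38 antibody. All three arms receive isatuximab, so that question concerns a mechanism they share. Protocol 4.3.3 gives the control arm a further purpose, to show what risk cemiplimab adds. For that purpose one would want the whole group of hemolytic events compared across arms, whether or not a transfusion came first. Safety and tolerability are the first co-primary objective (Protocol 9.1), so a complete count of a prespecified event group is a reasonable expectation.

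**Working it through.** The plan states no figure that this point depends on, so the check compares the text.

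**1. How the SAP treats similar groups (2.1.4.1 and 2.4.5.2).**

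| Event group | Full count planned? | Timed subset planned? | Window stated in 2.1.4.1? |
|---|---|---|---|
| Hemorrhage | Yes, by grade ("Hemorrhages as defined in" 2.1.4.1) | Yes, first event within 8 days after Grade 4 thrombocytopenia | Yes |
| Hypersensitivity/CRS CMQ (infusion reactions) | Yes, at any time | Yes, within 24 hours of infusion start | Yes |
| Hemolytic disorders | No | Yes, within 8 days after transfusion | No |

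Hemolysis is the only one of the three with the subset and no full count, and the only one whose window first appears in the analysis section.

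**2. Where each kind of event is reported.**

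- *Hemolytic TEAE with a transfusion in the preceding 8 days:* in the dedicated summary, the general TEAE tables and the listing. This holds whatever the cause, so a drug-caused event inside the window is kept.
- *Hemolytic TEAE with no transfusion in the preceding 8 days:* not in the dedicated summary. It is in the by-arm tables of all TEAEs (SOC/HLGT/HLT/PT and SOC/PT), in the drug-related table if judged related, and in the listing as worded.
- *Hemolysis that itself leads to a transfusion:* onset comes before that transfusion, so the event falls outside the window unless an earlier transfusion happens to cover it.

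**3. Whether the general tables can supply the missing count.** Not exactly. A patient with two hemolytic preferred terms appears in two PT rows, so adding rows can overstate the number of patients. HLT and HLGT rows count a patient once, but they follow the MedDRA hierarchy and not the CMQ. The tables limited to terms seen in at least 5% of patients in any arm give little help: with 35 patients per arm, one patient is 1/35 = 2.9% and two are 2/35 = 5.7%, so a term seen in no more than one patient per arm does not appear there.

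**4. Size.** The share of hemolytic events left out depends on how often patients are transfused and how onset relates to transfusion. The documents give neither. The share could be anything from none to all.

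**The case against.** The strongest reply is that little is lost. The excluded events are in by-arm tables at four MedDRA levels. The listing carries no window and holds the fields needed to judge each case, and with 35 patients per arm a listing is workable for an uncommon event. Anemia has shift tables and indirect Coombs results have their own summary (2.4.5.4, 2.4.5.7). Immune-related events have separate by-arm analyses with no transfusion condition, two of which extend through the 90-day safety follow-up. All of this stands, and it is why the point is minor. It does not provide the pooled count: the sponsor's immune-related grouping is not itemized, so nobody can tell whether hemolytic terms are in it.

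Three stronger readings are tempting, and the documents do not support them.

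- *That the two SAP sections contradict each other.* One chooses the terms and the other adds a timing filter. The SAP does the same elsewhere. This is an unexplained narrowing.
- *That hemolysis caused by the study drugs drops out of by-arm reporting.* The filter works on timing and not on cause, and excluded events remain in the general tables.
- *That the documents point to a cemiplimab hemolysis risk which the summary would hide.* Protocol 4.1.2 says that the normal role of PD-1 "is to down-modulate unwanted or excessive immune responses, including autoimmune reactions", which is general biology and does not mention hemolysis. Protocol 4.2.2.1 names no hemolytic event among the immune-related events it reports. Protocol Appendix I says "Anti-CD38 may cause a small decrease in hemoglobin in vivo", but the same sentence adds that severe hemolysis was not seen in treated patients, and isatuximab is given in every arm. A difference between arms by the PD-1 route is a possibility a reader might infer. The plan presents no evidence for it.

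**Conclusion.** The point holds as a minor one. The dedicated hemolysis analysis is narrower, without explanation, than the selection it cites, and the plan contains no unrestricted CMQ-level hemolysis summary. What is lost is the pooled patient count by arm, while the individual events stay visible elsewhere. No magnitude can be given, because it would need a transfusion or hemolysis rate that the documents do not contain. The conclusion rests on reading 2.4.5.2 literally. The window may have been meant only for a transfusion-related sub-analysis, as with hemorrhage after thrombocytopenia, but the SAP does not say so. The primary efficacy comparison and the futility rule are unaffected.

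**What to change.** In the hemolytic-disorders entry of SAP 2.4.5.2:

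- Tabulate all TEAEs from the CMQ, as 2.1.4.1 selects them, by arm: one row for patients with any such event, then rows by PT, for all grades and Grade ≥3.
- Show onset within 8 days after a transfusion as a labelled sub-row, following the SAP's own layout for hemorrhage after Grade 4 thrombocytopenia, and state the window in 2.1.4.1 as well.
- Say that the listing covers every CMQ case, regardless of transfusion.

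The cost is a sentence or two of SAP text and a few table rows. Transfusions are already recorded in the eCRF (Protocol 1.1, note on the blood typing interference test), so no new data are needed.
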